8.0 TREATMENT MODIFICATIONS

8.1 Radiation Treatment Modifications

Modifications to the radiation treatment will be discussed with the Principal Investigator.

8.2 Off Study Criteria

8.2.1 Patients may be taken off study for the following non-medical or administrative reasons:

- Patient refuses the procedure or further treatment
- It is deemed in the patient's best interest as determined by the PI.
- Serious protocol violation as determined by the PI.

8.2.2 Development of a concurrent serious medical condition that precludes the completion of fiducial marker placement, radiation therapy or follow-up.

8.2.3 Tumor progression (if occurs during treatment, at the end of radiation therapy unless the completion of local therapy is not indicated)

8.2.4 Initiation of cytotoxic chemotherapy (if occurs during treatment, at the end of radiation therapy unless the completion of local therapy is not indicated)

8.2.5 Development of a concurrent serious medical condition during active treatment and not attributable to therapy that precludes the completion of active treatment.

8.2.6 The completion of 60 months (5 years) follow-up.

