6.0 TREATMENT PLAN

6.1 Study Design

Medically inoperable patients with node negative, peripherally located, biopsy proven NSCLC measuring ≤5 cm will be enrolled, stratified, and randomized to receive multi-fraction or single fraction SBRT.

Patients will be stratified by KPS into one of three groups (See Appendix IV) and treatment center. (100, 90, 80 and below).

Prior to SBRT delivery, patients will undergo baseline imaging using PET/CT and will undergo formal pulmonary function testing. Blood and

urine samples will also be formally collected and stored for future correlative studies.

Patients randomized to the multi-fraction arm will receive 3 high dose fractions of radiation to the primary lung tumor. Those randomized to the single fraction arm will receive a single high dose fraction using SBRT. Overall treatment time for one fraction is one day, for three fractions is 8-24 days. Treatment may start within 4 weeks after registration.

SBRT is a technique that allows for improved precision of radiation delivery. In order to deliver stereotactic radiotherapy, precise mechanisms of patient immobilization, tumor localization, and beam delivery are required and discussed in detail below.

Following SBRT delivery, imaging and pulmonary function studies will be regularly performed to monitor tumor status and toxicity. Blood and urine, samples may also be formally collected and stored, as described above, following SBRT and in the event of tumor recurrence such that correlative studies can be performed.

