12.0 STATISTICAL ANALYSIS

This is a phase II randomized study to compare incidence of RTOG grade 3 or higher toxicity associated with 2 different, established SBRT regimens for NSCLC.

Group sample sizes of 49 in group one (Gy x 3) and 49 in group two (Gy x 1) achieve 81% power to detect a difference between the group incidences of toxicity of 0.17. The incidence of toxicity in group one (the treatment group) is assumed to be 0.03 under the null hypothesis and 0.2000 under the alternative hypothesis. The proportion in group two (the control group) is 0.03. The test statistic used is the one-sided Z test with continuity correction and unpooled variance. The significance level of the test was targeted at 0.05. The significance level actually achieved by this design is 0.0037.

Descriptive statistics will be presented for each group. Incidence of toxicity will be compared using Z test. Disease free survival and overall survival will be compared between two groups using log-rank test statistics. Correlation analysis will be performed to explore the relationship between outcomes and toxicities with tumor biomarkers. The estimate of acute and long term toxicity associated with SBRT for NSCLC will be reported.

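### Section 8.2 does not separate stopping treatment from leaving the study, and its treatment-completion triggers can act only in the 20 Gy x 3 arm once treatment has begun

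*Combined protocol and SAP*

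**What the plan says.** Section 8.2 has a single list of off-study criteria. Three entries turn on treatment not being carried through:

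- 8.2.1, which is permissive and confined to non-medical or administrative reasons: "Patient refuses the procedure or further treatment".
- 8.2.2: "Development of a concurrent serious medical condition that precludes the completion of fiducial marker placement, radiation therapy or follow-up".
- 8.2.5: "Development of a concurrent serious medical condition during active treatment and not attributable to therapy that precludes the completion of active treatment".

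8.2.6 adds completion of 60 months of follow-up to the same list. Section 6.1 gives the treatment duration: "Overall treatment time for one fraction is one day, for three fractions is 8-24 days". The study calendar (7.0) sets toxicity and QOL visits over five years and does not say what happens to a patient who stops treatment early.

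Section 12.0 gives the design: "Group sample sizes of 49 in group one (Gy x 3) and 49 in group two (Gy x 1) achieve 81% power". The three-fraction rate is "assumed to be 0.03 under the null hypothesis and 0.2000 under the alternative hypothesis". For the single-fraction arm, "The proportion in group two (the control group) is 0.03". For the test, "The test statistic used is the one-sided Z test with continuity correction and unpooled variance". Section 12.0 names no analysis population and no rule for patients who leave early.

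**The concern.** Stopping treatment and ending observation are different events, and section 8.2 treats them as one. The consequence differs by arm. A patient given 30 Gy in one session has no further treatment to refuse and no course left incomplete. A patient between fractions in the 20 Gy x 3 arm can meet 8.2.1, 8.2.2 or 8.2.5 and, if off study ends follow-up, contribute no later toxicity data.

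The three-fraction arm is the one whose excess of grade 3 or higher toxicity the one-sided test is designed to detect. Only about 49 x 0.20 = 9.8 events are expected there under the alternative, so a few missing events would matter. QOL and survival comparisons would be exposed to the same unequal loss. Randomisation does not protect against exits that occur after it and depend on the schedule assigned.

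**Working it through.** **Reading the text.**

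1. Meaning of off study. Finishing five years of follow-up is itself an off-study criterion (8.2.6), so the plain reading is that off study ends follow-up. This is inferred; no sentence says it outright.
2. Where each trigger can act after first exposure. Refusing further treatment (8.2.1), the radiation limb of 8.2.2, and 8.2.5 need a course still in progress, so they apply to 20 Gy x 3 only. Refusal before any treatment, the principal investigator's judgement of best interest, serious violation, the follow-up limb of 8.2.2, progression (8.2.3) and chemotherapy (8.2.4) apply to both arms.
3. Overlap. 8.2.5 is limited to conditions that therapy did not cause. 8.2.2 covers the same failure to complete radiation without that limit.
4. Timing. Section 1.1.2 cites a median of 10.5 months to observed toxicity in an earlier phase II series, against a treatment window of 8-24 days.

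**Reproducing the plan's figure.** Inputs from section 12.0: 49 per arm, rates 0.20 and 0.03, one-sided 0.05. Enumerate both binomials and reject when

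(p1 - p2 - 0.5(1/n1 + 1/n2)) / sqrt(p1(1-p1)/n1 + p2(1-p2)/n2) > 1.645,

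with p1 and p2 the observed proportions. Exact power is 0.805 (stated 81%) and the actual level is 0.0037 (stated 0.0037). The design reproduces.

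**Sensitivity range.** Assume k three-fraction patients exit during treatment, each with probability q of a grade 3+ event that goes unrecorded. Neither k nor q is in the documents. The three-fraction rate becomes

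- counted event-free: (9.8 - qk)/49
- dropped from the denominator: (9.8 - qk)/(49 - k)

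For example, k = 5 and q = 0.5 counted event-free gives (9.8 - 2.5)/49 = 0.149. The observed count is treated as binomial at this averaged rate, and the other arm stays at 0.03. Each cell shows exact power, event-free / dropped:

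| k | q = 0.10 | q = 0.20 (arm average) | q = 0.50 |
|---|---|---|---|
| 2 | 0.789 / 0.792 | 0.773 / 0.775 | 0.717 / 0.719 |
| 4 | 0.773 / 0.818 | 0.737 / 0.787 | 0.607 / 0.670 |
| 5 | 0.764 / 0.817 | 0.717 / 0.776 | 0.545 / 0.615 |

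The dropped figures do not move smoothly with k because the test is discrete. With all randomised patients followed, power stays at 0.805.

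**The case against.** A reader might infer that toxicity is in fact being lost selectively from the three-fraction arm and that its toxicity will therefore be understated. The documents do not support that, for these reasons:

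- **The triggers are not aimed at toxicity.** 8.2.1 is discretionary and restricted to non-medical or administrative reasons, so stopping because of feeling unwell fits it poorly. 8.2.5 excludes conditions caused by therapy. Only 8.2.2 is open on attribution, and a concurrent condition is naturally read as intercurrent illness. That 8.2.2 makes a treatment-related condition a ground for leaving is one possible reading, not stated text.
- **Some events are captured anyway.** Section 10.4 requires serious adverse events during the study or within 30 days of the last procedure to be followed until they resolve or stabilise, or until death or alternative therapy. It does not cover new late events.
- **Other exits act in both arms**, several of them over five years, and may remove more patients than the short treatment window does.
- **The direction is not fixed.** A patient who stops after one or two fractions has had less dose and may be at lower risk. The calendar also schedules toxicity evaluations at the second and third treatments, which gives the three-fraction arm extra chances to record events.
- **The 10.5-month median is limited evidence.** It comes from a series that included central tumours, which this trial excludes. A median does not show that nearly all events come later, and late onset makes toxicity-driven exit within 24 days less likely.

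All of this stands, and it limits what can be said about size and sign. It does not remove the gap: the criteria have unequal exposure by arm, and the plan does not say that observation continues or how such patients are analysed.

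**Conclusion.** The point holds as a structural weakness. Read as written, section 8.2 allows primary-endpoint data to be lost after treatment starts through criteria that can operate in only one arm, and section 12.0 has no rule to contain this. It rests on reading off study as the end of follow-up, which 8.2.6 implies.

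The size is unknown. With 2 to 5 such patients counted event-free, power falls from 0.805 to 0.773-0.717 at average risk and to 0.717-0.545 at an assumed 50% risk. With 10% risk and exclusion from the denominator it is 0.792-0.818 at the values of k tabulated, so little or no loss. These are ranges under assumption and do not estimate what happened. A fixed bias against finding excess toxicity with 20 Gy x 3 is not established.

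The different scope of 8.2.2 and 8.2.5 is a separate drafting inconsistency that needs reconciling. The whole point merits correction because the remedy is cheap and the endpoint affected is the primary one.

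**What to change.** 1. In section 8.2, distinguish 'off protocol treatment' from 'off study'. State that every randomised patient who stops treatment early stays on the section 7.0 toxicity, QOL and survival schedule for five years unless consent to follow-up is withdrawn.
2. In section 12.0, state that these patients are analysed as randomised. Report numbers and reasons for early exit by arm, and add a sensitivity analysis for their unobserved toxicity. For patients already taken off study, the same tabulation and sensitivity analysis can still be done.
3. The sponsor should reconcile 8.2.2 with 8.2.5 on whether attribution to therapy matters; this review does not propose the wording.

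No rule on when to stop treatment needs to change. The cost is one amendment to 8.2 and 12.0, plus continued visits for a few patients. Some who stop treatment may accept only records-based follow-up, which would give less complete toxicity and QOL data.

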9.0 RESPONSE CRITERIA

This protocol will use a modified version of the international criteria proposed by the Response Evaluation Criteria in Solid Tumors (RECIST) Committee [JNCI 92(3): 205-216, 2000] See http://ctep.info.nih.gov/guidelines/recist.html for further details. Additional definitions beyond the RECIST guidelines specific to this protocol are incorporated to define local control as described below.

9.1 Baseline documentation of "Target" and "Non-Target" Lesions

Patients enrolled to this protocol should have clinical stage I (T1 or T2, N0, M0) or clinical stage II (non-small cell lung cancer. At time of treatment, they should only have one site of gross disease in the lung with no metastases. The primary lung tumor should be identified as the *target lesion* and recorded and measured at baseline and with each follow-up imaging evaluation.

The longest diameter (LD) for *the target lesion* will be calculated **from the treatment planning CT scan** using pulmonary windowing and reported as the baseline LD. The baseline LD will be used as reference by which to characterize the objective tumor. For follow-up assessment, diagnostic CT scans performed using a 5 mm contiguous reconstruction algorithm using pulmonary windowing taken as part of scheduled protocol follow-up are preferred as the method of evaluation for response. When CT scans are not available, chest x-ray determination will be allowed as long as the target lesion is clearly visible. Changes in serum tumor markers will not be allowed for assessment of either local tumor progression or metastatic progression.

Local treatment effects in the vicinity of the tumor target may make determination of tumor dimensions difficult. For example, bronchial or bronchiolar damage may cause patchy consolidation around the tumor that over time may coalesce with the residual tumor. In cases where it is indeterminate whether consolidation represents residual tumor or treatment effect, it should be assumed that abnormalities are residual tumor. A treating radiation oncologist will review films as well as a radiologist at each site.

All other lesions (or sites of disease) that appear after treatment (e.g., regional lymph nodes and distant metastases) should be identified as **non-target lesions** and should also be recorded at the point of their appearance and with each follow up. Non-target lesions should constitute measurable disease, which by definition requires having an appearance suspicious for carcinoma and having a dimension of at least 1.0 cm. Assessment of regional lymphatic or metastatic progression will be made in comparison to the required pretreatment staging studies or any other pretreatment imaging evaluations available. Only non-target lesions appearing at the margin of the PTV (i.e., within 1.0 cm) will have recorded measurements (see Marginal Failure in the table below). Recorded measurements of all other non-target lesions are not required, but the presence or absence of each should be noted throughout follow-up.

٦

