9.2 Response Criteria

Г

Evaluation of Tar	get Lesions
Complete Response (CR)	Disappearance of the target lesion; ideally, this determination will be made based on CT image evaluation.
Partial Response (PR)	At least a 30% decrease in the LD of the target lesion, taking as reference the baseline LD; ideally, this determination will be made based on CT image evaluation.
Stable Disease (SD)	Neither sufficient shrinkage to qualify for CR/PR above nor sufficient increase to qualify for LE below, taking as reference the smallest LD since the treatment started
Local Enlargement (LE)	At least a 20% increase in the LD of target lesion, taking as reference the smallest LD recorded since the treatment started; Ideally, this determination will be made based on CT image evaluation.
Local Failure (LF)	Refers to the primary treated tumor after protocol therapy and corresponds to meeting both of the following two criteria: 1) Increase in tumor dimension of 20% as defined above for local enlargement (LE); 2) The measurable tumor with criteria meeting LE should be avid on Positron Emission Tomography (PET) imaging with uptake of a similar intensity as the pretreatment staging PET, OR the measurable tumor should be biopsied confirming viable carcinoma. For outcome analysis, Marginal Failures (MF; see below) will also be counted as LF; however, they should be distinguished specifically as MF, not LF, on all report forms. The EORTC criteria for post-treatment PET evaluation will be used as a basis for evaluation in cases more difficult to assign as to whether the uptake is pathological for cancer recurrence vs. inflammation. ⁴⁶
Local Control (LC)	The absence of Local Failure.
Progressive Disease (PD)	Progression will be defined by any

imaging and clinical findings which
support development of disease outside
the chest, in the mediastinum or first
echelon lymph nodes, and by PET +/-
biopsy consistent with progression at the
target lesion.

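### Section 9.1 names two image readers, masks neither and does not say whose read is used for outcome analysis, which leaves avoidable room for detection bias in the local-failure and patterns-of-failure comparisons

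*Combined protocol and SAP*

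**What the plan says.** Section 9.1 of the protocol sets the readers: "A treating radiation oncologist will review films as well as a radiologist at each site". No section of the combined document masks either reader, provides central review, or says which read is used when the two differ.

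The same section acknowledges that reading is hard after SBRT: "Local treatment effects in the vicinity of the tumor target may make determination of tumor dimensions difficult". It then gives a default: "In cases where it is indeterminate whether consolidation represents residual tumor or treatment effect, it should be assumed that abnormalities are residual tumor". It also allows a second modality: "When CT scans are not available, chest x-ray determination will be allowed as long as the target lesion is clearly visible".

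Section 9.2 defines local failure by two criteria that must both be met. The first is growth of at least 20% in longest diameter (LD), measured from the smallest value recorded since treatment started. The second is PET avidity "with uptake of a similar intensity as the pretreatment staging PET, OR the measurable tumor should be biopsied confirming viable carcinoma". For hard PET cases it says "The EORTC criteria for post-treatment PET evaluation will be used as a basis for evaluation in cases more difficult to assign". Marginal failures count as local failures in the outcome analysis. Progressive disease is defined more loosely, from imaging and clinical findings, with PET and optional biopsy at the target lesion.

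Under the Section 7.0 footnotes, follow-up PET-CT is fixed only at 6 months. Later PET-CT, and any follow-up biopsy, depend on clinical indication.

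Section 2.2.1 makes patterns of failure and disease-free survival (DFS) secondary between-arm objectives. Section 12.0 compares DFS by log-rank test.

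**The concern.** Sections 6.1 and 6.2.1.2 set one fraction against three, with no sham or masking. That a treating radiation oncologist knows the arm is an inference from this design, but a safe one. The radiologist may or may not know it, because the protocol is silent.

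Outcomes that need judgement are thus read by at least one person who ordinarily knows the arm, and the data going into the analysis are not tied to either reader. If the readers disagree, sites can settle the matter in different ways, and nothing requires both reads to be kept. If error in reading differs by arm, it goes straight into local failure and patterns of failure.

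Section 1.1.4 says that no earlier study has compared the two regimens for efficacy and toxicity, so these secondary comparisons are likely to be cited. The weakness can be avoided because the protocol already requires a reader who could work without knowing the arm.

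**Working it through.** **The plan's own figures.** The documents give no event rate, power or alpha for local failure or DFS. The only design calculation (Section 12.0) is for toxicity: 49 per arm, 0.20 against 0.03, one-sided Z test with continuity correction and unpooled variance. Exact enumeration of the 50 × 50 possible outcomes gives alpha 0.0037 (stated 0.0037) and power 80.5% (stated 81%). Those figures stand, and this point does not touch them.

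**Where judgement remains.** Setting each rule against what it leaves open:

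| Step | Rule in Sections 9.1 and 9.2 | What stays open |
|---|---|---|
| LD within consolidation | Indeterminate change counts as residual tumor | Who decides that a case is indeterminate |
| Local enlargement | At least 20% above the smallest LD recorded | The LD measurement itself; one low earlier value lowers the threshold |
| PET criterion | Uptake similar to the pretreatment scan; EORTC criteria as a basis in hard cases | Who judges similarity; Section 9.2 itself foresees "cases more difficult to assign as to whether the uptake is pathological for cancer recurrence vs. inflammation" |
| Biopsy criterion | Viable carcinoma confirmed | Little, once a biopsy has been taken |
| Progressive disease | Supporting imaging and clinical findings | No size threshold; no named reader |

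**Illustration of leverage.** Inputs: 49 patients per arm (Section 12.0); two-year local control of 95% in a phase II study of 60 to 66 Gy in three fractions (Section 1.1.2); and, from two single-dose series (Section 1.1.3), a two-year local progression-free rate of 78% and 24-month local control of 67.9%. The number of changed calls, two, is an assumption, because the documents give no disagreement rate.

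- Shift in the arm's proportion: 2 / 49 = 4.1 percentage points.
- Failures at 95%: (1 − 0.95) × 49 = 2.45. Two calls are 2 / 2.45 = 82% of that count.
- Failures at 78%: (1 − 0.78) × 49 = 10.78. Two calls are 2 / 10.78 = 19%.
- Failures at 67.9%: (1 − 0.679) × 49 = 15.73. Two calls are 2 / 15.73 = 13%.

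These counts treat every patient as followed for two years. The 95% is a Kaplan-Meier estimate from a study with two-year overall survival of 54.7%, so the failures actually observed in an arm of 49 would be fewer than 2.45. That study also included central tumors, which Section 3.2 excludes here. The single-dose series mixed doses, and the one giving 78% was mostly metastases (48 of 59 patients). None of the three is a forecast for this trial.

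**DFS.** No figure can be derived. The documents do not define a DFS event and give neither an event count nor a hazard ratio.

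**The case against.** The strongest reply is that the protocol already constrains the reading. Indeterminate consolidation is resolved one way in both arms, and local failure needs measured growth together with PET or biopsy evidence. A radiologist is involved at every site, and two site readers are a reasonable choice for a phase II trial whose primary endpoint is toxicity. Much of this stands. It keeps the point to the secondary endpoints and makes it an improvement rather than a defect in the main analysis. It does not say whose measurement is analysed, and it does not mask that measurement.

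Some stronger readings are tempting but unsupported:

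- **A reader might infer that local failure and DFS simply follow the unmasked oncologist's opinion.** The documents give neither reader precedence, and the two-part definition of local failure restricts what opinion alone can do. The link to DFS is indirect.
- **A reader might infer that the oncologist favours a regimen he or she selected.** Assignment is randomized (Section 6.1), and Section 9.1 speaks of a treating radiation oncologist without saying that this is the person who treated that patient. Section 1.1.4 describes control as excellent with both regimens, so no direction of bias is indicated.
- **A reader might infer that two calls could nearly double or erase an arm's failures.** That holds only at 95% control. At the cited single-dose figures, two calls are 13% to 19% of the count.
- **A reader might infer a route to the primary endpoint**, because Section 8.2.3 lists progression among the off-study criteria. The documents do not say that toxicity assessment then stops, so no such effect is claimed.

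**Conclusion.** The concern holds in a limited form. Neither reader is masked, one will ordinarily know the arm, and the read used for outcome analysis is unspecified. Avoidable detection bias is therefore possible in local failure and patterns of failure, and indirectly in DFS. The primary toxicity comparison and overall survival do not depend on these reads.

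Size and direction cannot be determined from the documents. The 4.1 points rest on an assumed two changed calls in one arm. The weight of those calls depends on a failure count that ranges from about 2.5 to about 16 per arm across the rates the protocol cites. The conclusion also rests on the inference that a treating oncologist knows whether one or three fractions were given.

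This is a cheap improvement. It does not invalidate the design.

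**What to change.** Amend Section 9.1 along these lines:

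> *For outcome analysis, the site radiologist measures LD and judges local enlargement, PET avidity and new lesions, working from an imaging request that omits dose and number of fractions. The radiologist is given the baseline LD and the PTV outline without dose information. This read governs the imaging component of local failure, marginal failure and progressive disease. The treating radiation oncologist's read is recorded separately as supporting information.*

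The planning data are needed because baseline LD comes from the planning CT, and lesions at the PTV margin are judged within 1.0 cm of the PTV. The residual-tumor default and the EORTC PET criteria stay and are applied by the governing reader. Biopsy results and the clinical-findings part of progressive disease remain as Section 9.2 defines them. The amendment concerns only which read is analysed and changes nothing in patient management.

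The cost is a short amendment, a standard imaging request and a small extra step to prepare the PTV outline. No new reader or visit is needed. Masking will be imperfect, because a radiologist could open the chart. Even so, naming the governing read in advance removes the ambiguity, and keeping both reads lets disagreement be reported by arm. The missing definition of a DFS event is a separate gap that this change does not close.
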